9.4.4 Supportive analyses

In addition to the primary analysis, the primary efficacy variable will also be analyzed using the same primary analysis model in the PP population as supportive.

A supplemental log-rank test will be performed for both the FAS and the PP population. Survival function for each treatment group will be estimated by Kaplan-Meier method and the Kaplan-Meier curves will be presented for both the FAS and the PP populations.

The frequency and percentage of patients who reach the primary composite endpoint will be provided by treatment group for both the FAS and the PP population.

Additionally, similar analyses will be performed for each of the components of the composite endpoint with all events for that component that occurred during the double-blind treatment epoch of the study to quantify the strength of the effect for each component in the primary composite endpoint.

9.5 Analysis of secondary variables

9.5.1 Efficacy variables

In the core part, FAS will be used for the following key and other secondary analyses for efficacy endpoints.

A cut-off data analysis will be carried during the OLE epoch after all patients have been enrolled into the OLE, and completed Visit 304 (Month 4) or discontinued.

The cut-off date is defined as the latest of Visit 304 date or discontinuation date (the last visit prior to Visit 304). All data on or prior to this cut-off date during the OLE epoch will be used

for analysis. [REDACTED]

9.5.1.1 Changes in NT-proBNP from baseline at pre-defined time points (Weeks 4 and 8, Month 6)

Described in [Section 9.5.1.10 Biomarkers](#).

9.5.1.2 Time to the first occurrence of CV death, HF hospitalization or intensification of treatments due to documented episode(s) of worsening HF

In the core part, it will be analyzed using the same Cox proportional hazards model used for the primary endpoint. Analysis will be repeated for each of the components of the composite endpoint.

The analysis above will not be applied for the OLE epoch.

9.5.1.3 NYHA classification

In the core part, the change from randomization to each of the post-randomization visits in NYHA classification will be analyzed using Cochran-Mantel-Haenszel test for different row (treatment) means, stratified for screening NT-proBNP classification, based on the modified ridit scores which are also referred to as the standardized mid-ranks.

In the OLE epoch, the change from baseline (Visit 301) to each of the post baseline visits in NYHA classification will be summarized. FAS-Ext will be used, and analyses will be done by the treatment arm in the double-blind treatment epoch. Additionally, analyses will be repeated for subset of FAS-Ext with only patients in the LCZ arm of the double-blind treatment epoch, throughout the period from run-in epoch to OLE epoch using Visit 101 as baseline.

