--	--

Study design	
This study is a multicenter, randomized, double-blind, double-dummy, parallel-group, active-controlled study to assess the effect of LCZ696 and enalapril on CV mortality and morbidity reduction in Japanese HF patients with reduced ejection fraction.
 
The core part above is followed by the optional OLE in which patients are treated with open-label LCZ696 to assess the long-term safety and tolerability of LCZ696 treatment.

Population	
Male or female patients with CHF (NYHA class II-IV), aged 20 years or older with LVEF \leq 35%. Approximately 220 patients (110 patients in each arm) will be randomized.
 
All participants of the core part who are eligible to receive study drug will be offered the option to enter the OLE. It is anticipated that approximately 180 patients will complete the core part of the study and that the majority of them will be enrolled into the OLE.

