2.2 Secondary objectives

2.2.1 Key secondary objectives

- To assess the effect of LCZ696 100 mg b.i.d. and 200 mg b.i.d. on changes in NT-proBNP from baseline at predefined time points (Weeks 4, 8 and Month 6)
- To assess the effect of LCZ696, compared to enalapril, on delaying the time to first occurrence of CV death, HF hospitalization, or intensification of treatments due to documented episode(s) of worsening HF defined as: worsening signs and symptoms of HF requiring addition of a new drug for HF treatment, initiation of IV treatment, increase of diuretic dose for persistent use for ≥ 4 consecutive weeks, or institution of mechanical or circulatory support such as mechanical ventilation, ultrafiltration, hemodialysis, intra-aortic balloon pump or ventricular assist device
- To assess the effect of LCZ696, compared to enalapril, on changes in NYHA classification from baseline at predefined time points (Weeks 4, 8 and Month 6)
- To assess the effect of LCZ696, compared to enalapril, on improving the clinical summary score for HF symptoms and physical limitations, as assessed by the Kansas City Cardiomyopathy Questionnaire (KCCQ) at predefined time points (Week 8 and Month 6)
- To assess safety and tolerability of LCZ696 compared to enalapril

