4.1 Inclusion criteria

Patients eligible for inclusion in the core part have to fulfill all of the following criteria:

1. Written informed consent must be obtained before any assessment is performed.
2. Outpatients ≥ 20 years of age (at the time of signing informed consent), male or female.
3. Patients with a diagnosis of CHF NYHA class II-IV and reduced ejection fraction:
 - LVEF $\leq 35\%$ at Visit 1 (any local measurement, made within the past 6 months using echocardiography, MUGA, CT scanning, MRI or ventricular angiography is also acceptable, provided no subsequent measurement above 35%)
 - NT-proBNP ≥ 600 pg/ml at Visit 1 **OR** NT-proBNP ≥ 400 pg/ml at Visit 1 and a hospitalization for HF within the last 12 months (according to central laboratory measurements)
4. Patients must be on an ACEI or an ARB at a stable dose for at least 4 weeks before Visit 1.
5. Patients must be treated with a β -blocker, unless contraindicated or not tolerated, at a stable dose for at least 4 weeks prior to Visit 1 (reason should be documented if patients reported contraindications or intolerance).
6. An aldosterone antagonist should also be considered in all patients, taking account of renal function, serum potassium and tolerability. If given, the dose of aldosterone antagonist

should be optimized according to guideline recommendations and patient tolerability, and should be stable for at least 4 weeks prior to Visit 1. Other evidence-based therapy for HF should also be considered e.g. cardiac resynchronization therapy and an implantable cardioverter-defibrillator in selected patients, as recommended by guidelines.

Patients eligible for inclusion into the open-label extension must fulfill the following criteria:

7. Written informed consent for the open-label extension must be obtained before any assessment is performed.
8. Patients who have completed the double-blind treatment epoch and are able to be safely enrolled into the OLE as judged by the investigator.

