5.3 Treatment assignment, randomization

At Visit 201, all eligible patients will be randomized via Interactive Response Technology (IRT) to one of the treatment arms. The investigator or his/her delegate will contact the IRT after confirming that the patient fulfills all the inclusion/exclusion criteria. The IRT will assign a randomization number to the patient, which will be used to link the patient to a treatment arm and will specify a unique medication number for the first package of investigational treatment to be dispensed to the patient. The randomization number will not be communicated to the caller.

The randomization numbers will be generated using the following procedure to ensure that treatment assignment is unbiased and concealed from patients and investigator staff. A patient randomization list will be produced by the IRT provider using a validated system that automates the random assignment of patient numbers to randomization numbers. These randomization numbers are linked to the different treatment arms, which in turn are linked to medication numbers. A separate medication list will be produced by or under the responsibility of Novartis Drug Supply Management using a validated system that automates the random assignment of medication numbers to packs containing the investigational drug(s).

Randomization will be stratified by the level of NT-pro BNP obtained at Visit 1 (\geq or < 1600 pg/ml).

No randomization process will be applied to the OLE epoch. During the OLE, all patients will be treated with LCZ696. IRT system will be used to enroll patients into the OLE epoch and dispense study drug in the same manner as in the randomized treatment epoch described above.

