9.5.1.4 KCCQ

The KCCQ instrument includes several domains. Only the domains that address HF symptoms and physical limitations will be analyzed. The clinical summary score of KCCQ is computed as the mean of the available domain scores of total HF symptom and physical limitation. The clinical summary score of KCCQ will be analyzed based on a repeated measures ANCOVA model in which treatment, screening NT-proBNP classification, visit, and treatment-by-visit interaction will be included as fixed-effect factors and baseline value as a covariate, with a common unstructured covariance for each treatment arm. The analysis will be performed based on all available data and based on likelihood method. The estimated treatment effect with the corresponding confidence interval will be provided. The primary treatment comparison between LCZ696 and enalapril is to be made at Week 8 and Month 6.

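### The key secondary NYHA test is valid but usually less precise than it could be, because it does not stratify by NYHA class at randomization

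*Protocol*

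**What the plan says.** In Protocol section 9.5.1.3, "the change from randomization to each of the post-randomization visits in NYHA classification will be analyzed using Cochran-Mantel-Haenszel test" for different treatment means. The test is "stratified for screening NT-proBNP classification, based on the modified ridit scores which are also referred to as the standardized mid-ranks". No other stratum or covariate is named.

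NYHA change at Weeks 4, 8 and Month 6 is a key secondary objective (section 2.2.1) and a key secondary endpoint (section 6.4.1). Table 6-1 and its footnote 15 schedule NYHA at Visit 201 for all patients to be randomized.

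The other key secondary endpoints with a measured baseline are adjusted for it. For KCCQ, treatment, NT-proBNP class, visit and their interaction "will be included as fixed-effect factors and baseline value as a covariate" (section 9.5.1.4). NT-proBNP and the other biomarkers use the log baseline value as a covariate (section 9.5.1.10).

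"Randomization will be stratified by the level of NT-pro BNP obtained at Visit 1" (section 5.3), so NYHA balance between arms is left to chance. The planned size is stated in the protocol summary: "Approximately 220 patients (110 patients in each arm) will be randomized".

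**The concern.** Subtracting the baseline is not the same as adjusting for it. NYHA is a bounded four-class scale: a class I patient cannot improve and a class IV patient cannot worsen. Regression to the mean also pulls high classes down and low classes up, whatever the treatment. Ranking all changes together within an NT-proBNP stratum leaves that spread in the variance of the test. It also leaves the observed result open to chance imbalance in starting class.

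At stake is the precision of one supportive endpoint in a trial of about 220 patients that was sized on feasibility. Section 3.2 says its aim is to see a trend like that of the earlier global outcome trial.

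**Working it through.** **1. The plan's own figure.** The protocol states no effect size or power for NYHA. Its sizing (section 9.7) concerns the primary endpoint and reproduces:

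- P(HR < 1) = Φ(√57/2 × |ln 0.8|) = Φ(3.775 × 0.2231) = Φ(0.842) = 80.0%. The events needed for 80% are 56.9.
- 220 patients, 22 months of accrual and 40 months in total give 57.0 events if 13% is an annual probability, and 53.8 if 0.13 is a hazard.

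So N = 220, 1:1, is the right frame for the NYHA test, but nothing in the sizing speaks to it.

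**2. Inputs for NYHA.** From the protocol: 110 per arm, two NT-proBNP strata, a change score, modified ridits. Not in the protocol: the class mix at randomization and the baseline to follow-up correlation. Section 4.1 gives only the eligible range ("Patients with a diagnosis of CHF NYHA class II-IV and reduced ejection fraction"). Both are therefore assumed and varied.

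**3. Normal-theory guide.** With equal variances and correlation ρ, the efficiency of a change score relative to baseline adjustment is (1+ρ)/2, so the loss is (1−ρ)/2.

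| ρ | 0.3 | 0.4 | 0.5 | 0.6 | 0.7 | 0.8 | 0.9 |
|---|---|---|---|---|---|---|---|
| Loss | 35% | 30% | 25% | 20% | 15% | 10% | 5% |

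For scale, at ρ = 0.4 the effective size is 220 × 0.70 = 154, and at ρ = 0.6 it is 220 × 0.80 = 176.

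**4. Simulation of the planned test.** Assumptions: N = 220, latent-normal NYHA, treatment shift 0.5 latent SD, 3,000 trials per setting. The planned test is compared with one stratified by NT-proBNP × NYHA class at randomization. Relative efficiency is the ratio of (mean z / SD z)², and the loss is one minus that ratio. A negative loss favors the planned test.

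| Class mix at randomization | Loss, latent correlation 0.3 | Loss, latent correlation 0.9 |
|---|---|---|
| 95% II, 5% III | 11% | −5% |
| 90% II, 10% III | 18% | −2% |
| 5% I, 85% II, 10% III | 25% | 2% |
| 70% II, 29% III, 1% IV | 30% | 7% |
| 5% I, 70% II, 24% III, 1% IV | 34% | 10% |
| 50% II, 45% III, 5% IV | 32% | 9% |

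Power, planned versus NYHA-stratified:

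- 0.84 versus 0.92 (70% II, latent correlation 0.5)
- 0.92 versus 0.95 (70% II, 0.7)
- 0.88 versus 0.89 (90% II, 0.7)

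**5. The pooled strata proposed here.** The grid in step 4 separates every NYHA class. A further simulation used I/II versus III/IV, with mixes of about 4/74/20/2% and 3/62/33/2%, a shift of 0.35 latent SD, correlations of 0.4 to 0.8 and 2,500 trials per setting.

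- Relative efficiency of the stratified test, here the squared ratio of mean z, was 1.23 to 1.47. That is a loss for the planned test of 1 − 1/1.23 = 19% to 1 − 1/1.47 = 32%.
- One-sided null rejection was 2.2-2.8% against a nominal 2.5%.

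A wider set, including only about 10% in class III, gave 0.99 to 1.44 with null rejection still close to nominal. Pooling gives nearly the same gain as separate classes, except that it recovers somewhat less when some patients are class I at randomization.

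**6. Chance imbalance.** If 25% are class III/IV (assumption), the SD of the between-arm difference in that share is √(0.25 × 0.75 × 2/110) = 0.058, about 6 percentage points.

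**The case against.** The best case for the plan has five parts.

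- **The test is valid.** It already stratifies by the only randomization factor, and adding a stratum is a choice rather than a correction. This stands: the point is about efficiency. A reader might infer bias or an inflated error rate, and the documents support neither.
- **The comparison with KCCQ and biomarkers is selective.** Those are continuous and modelled by ANCOVA. The closer relative is the clinical composite score (section 9.5.1.6), which uses the same CMH test with the same single stratum. That is fair: the ordinal endpoints are handled alike. It weakens the charge of inconsistency but does not restore the lost precision.
- **Imbalance is covered.** Section 9.2 lists NYHA among the baseline characteristics and allows supplemental analyses after a substantial imbalance. That provision is optional and triggered by the data, and it leaves the planned test unchanged.
- **Strata could be thin.** With 10% in class III/IV, 22 patients over two NT-proBNP strata and two arms leave 22/4 = 5.5 per cell before deaths and missed visits. This is a real but small cost; the simulated error rate stayed near nominal in that setting.
- **Detail belongs in the SAP.** The SAP is not at hand, but section 9.5.1.3 itself names the test, the scores and the stratum, so this is a stated choice and not a gap.

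**Conclusion.** The point holds as a modest efficiency improvement. The planned NYHA test usually gives up information that the trial already collects. The loss is roughly 0-35%, depending on a class mix and a correlation that the protocol does not state. It is largest for a mixed class II/III population with low to moderate correlation. It vanishes, or turns slightly in favor of the planned test, when nearly all patients are class II and NYHA hardly moves.

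Three stronger readings are tempting and not supported:

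- A fixed loss of about 20-30% needs a correlation of about 0.4-0.6 in the formula, or a mixed population in the simulation; neither is given in the documents.
- The planned choice cannot be said to have no benefit anywhere, since it did marginally better in the near-homogeneous, stable settings.
- The trial's conclusion is not at risk: section 9.4.2 judges the primary objective on the hazard ratio point estimate alone. The effect is confined to the precision of one key secondary endpoint.

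**What to change.** In section 9.5.1.3, state before unblinding that the CMH test is stratified by screening NT-proBNP (<1,600, ≥1,600 pg/mL) crossed with NYHA class at randomization (I/II versus III/IV), with modified ridits computed within strata. Keep the NT-proBNP-only version as a sensitivity analysis.

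The cost is one sentence in the protocol or SAP. The Visit 201 class is already recorded, so no new data are needed. The one downside is thinner strata if few patients are in class III/IV.

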9.5.1.4 KCCQ

The KCCQ instrument includes several domains. Only the domains that address HF symptoms and physical limitations will be analyzed. The clinical summary score of KCCQ is computed as the mean of the available domain scores of total HF symptom and physical limitation. The clinical summary score of KCCQ will be analyzed based on a repeated measures ANCOVA model in which treatment, screening NT-proBNP classification, visit, and treatment-by-visit interaction will be included as fixed-effect factors and baseline value as a covariate, with a common unstructured covariance for each treatment arm. The analysis will be performed based on all available data and based on likelihood method. The estimated treatment effect with the corresponding confidence interval will be provided. The primary treatment comparison between LCZ696 and enalapril is to be made at Week 8 and Month 6.

9.5.1.5 Composite of (total) HF hospitalizations and CV death

The composite endpoint of recurrent hospitalizations (including the first) due to HF and death due to CV during the double-blind period will be analyzed using a negative binomial model ([McCullagh and Nelder 1989](#)) with the count data as the dependent variable, treatment group and the stratification factor screening NT-proBNP as fixed-effect factors, and log(follow-up duration) as the off-set. The estimated event rates (intensities/risk rate) and their 95%

confidence intervals will be provided by treatment group. The treatment comparison will be performed through the estimated ratio of risk rates.

9.5.1.6 Clinical composite score

The clinical composite score will be analyzed at all time-points when both NYHA classification and Global Assessment are measured, using Cochran-Mantel-Haenszel (CMH) test for different row (treatment) means, stratified for screening NT-proBNP classification, based on the modified ridit scores which are also referred to as the standardized mid-ranks.

9.5.1.7 Time to all-cause death

It will be analyzed using the same Cox proportional hazards model used for the primary endpoint.

9.5.1.8 Hospitalizations (all-cause and cause-specific)

It will be analyzed using the same negative binomial model for the composite endpoint of total HF hospitalizations and CV death described in [Section 9.5.1.5](#). Analysis will be performed for all-cause hospitalizations and cause-specific hospitalizations as well.

Time to the first occurrence of hospitalization will be analyzed using the same Cox proportional hazards model used for the primary endpoint. Analysis will be performed for all-cause hospitalizations and cause-specific hospitalizations as well.

9.5.1.9 Echocardiogram

Summary statistics for change from baseline (Visit 301) of echo parameters will be presented. FAS-Ext will be used, and analyses will be done by the treatment arm in the double-blind treatment epoch.

Pearson's correlation coefficient and its two-sided 95% confidence interval between change in NT-proBNP and change in structural cardiac measurements (LV end systolic and diastolic volume indices, LVEF, and LA volume index) from baseline (Visit 301) to Month 12 will be analyzed. Similarly spearman's correlation coefficient and its two-sided 95% confidence interval will be analyzed.

Above analysis is repeated for change in log transformed NT -proBNP.

9.5.1.10 Biomarkers

In the core part, for the treatment comparisons of LCZ696 vs enalapril, change from baseline (Visit 101) to the pre-defined time-points in logarithmic scale will be analyzed using a repeated measures ANCOVA model with treatment, the stratification factor screening NT-proBNP, visit and treatment-by-visit interaction as fixed effect factors and the logarithmic baseline biomarker value as a covariate, with a common unstructured covariance matrix among visits for each treatment. The estimated treatment effects in terms of ratios of geometric means, based on the least-squared means for within and between treatment groups from the ANCOVA model, and the corresponding two-sided 95% confidence intervals will be provided. The analysis will be performed based on all available data in the FAS and based on likelihood method with an assumption of missing at random for missing data. Descriptive

summary statistics (mean, median, standard deviation, min, max, Q1, Q3, geometric mean, 95% CI for geometric mean) for the change from Visit 101 to each post-baseline visit will be presented. Graphical mean plots with 95% CIs will also be provided.

Analysis will be conducted for all of the FAS population with relevant biomarker measures.

To characterize the effect of the two LCZ696 dosages (100 mg b.i.d., 200 mg b.i.d.) on NT-proBNP, the estimates of ratio from baseline (Visit 101) at Week 4 and Week 8 of LCZ696 treatment arm from the ANCOVA model described above are presented, and comparison of change from baseline at each dose level will be made using a t-test. Descriptive summary statistics for the changes from Visit 199 to post-randomization visits (Visits 202, 203, 204, 206) will be presented for LCZ696 treatment arm. In addition, descriptive summary for the change from Visit 199 to Visit 206 (Month 6) will be summarized by actual dose level immediately prior to Visit 206 for LCZ696 treatment arm. Graphical mean plots with 95% CIs will be provided as well. Analysis will be conducted for all of the FAS population with NT-proBNP measures. Same analysis will be conducted for the patients who did not require any dose adjustment(s) up to Week 8 in the FAS population with NT-proBNP measures. Analysis described above will be repeated for the subgroups, defined by the stratification for randomization – screening NT-proBNP (< 1,600 pg/mL, \geq 1,600 pg/mL).

For reference, same analysis will be performed for enalapril treatment arm to characterize the effects of enalapril dosages (5 mg b.i.d., 10 mg b.i.d.).

In the OLE epoch, for biomarkers, descriptive summary statistics (mean, median, standard deviation, min, max, Q1, Q3, geometric mean, 95% CI for geometric mean) for the change from baseline (Visit 301) to each post-baseline visit will be presented. FAS-Ext will be used, and analyses will be done by the treatment arm in the double-blind treatment epoch. Additionally, analyses in NT-proBNP will be repeated for subset of FAS-Ext with only patients in the LCZ arm of the double blind treatment epoch, throughout the period from run-in epoch to OLE epoch biomarker visits (Visits 301, 302, 303, 304 and 306) using Visit 101 as baseline.

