6.4.3 Heart failure symptoms reduction and reduction in physical limitation

The KCCQ is a self-administered questionnaire and requires, on average, 4-6 minutes to complete. It contains 23 items, covering physical function, clinical symptoms, social function, self-efficacy and knowledge, and Quality of Life (QoL), each with different Likert scaling wording, including limitations, frequency, bother, change in condition, understanding, levels of enjoyment and satisfaction. A change of 5 points on the scale scores, either as a group mean difference or an intra-individual change appears to be clinically significant. The KCCQ is a valid, reliable and responsive health status measure for patients with CHF and may serve as a clinically meaningful outcome in CV clinical research, patient management and quality assessment ([Green et al. 2000](#)).

The HF symptoms and physical limitation domains scores show the best the correlation for improvements following a CHF exacerbation ([Green et al. 2000](#)). Thus, one of the secondary endpoints is a clinical summary score based on the HF symptoms and physical limitation domains scores of the KCCQ at 6 months. The KCCQ questionnaire will be completed at Visits 201, 204, 206, 209, 212, and 299 (EOS).

In the OLE epoch, the KCCQ will not be assessed.

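### The repeated-measures models for NT-proBNP and KCCQ impose one baseline slope on all visits; a baseline-by-visit term would protect precision at almost no cost

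*Protocol*

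**What the plan says.** Protocol 9.5.1.10 (Biomarkers) analyses change from Visit 101 on the log scale by repeated-measures ANCOVA. The terms are treatment, the screening NT-proBNP stratum, "visit and treatment-by-visit interaction as fixed effect factors and the logarithmic baseline biomarker value as a covariate". The covariance is specified "with a common unstructured covariance matrix among visits for each treatment", and estimation is "based on likelihood method with an assumption of missing at random for missing data". The key secondary NT-proBNP time points are Weeks 4 and 8 and Month 6 (2.2.1 and 9.5.1.1).

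Protocol 9.5.1.4 (KCCQ) uses the same form for the clinical summary score: "treatment, screening NT-proBNP classification, visit, and treatment-by-visit interaction will be included as fixed-effect factors and baseline value as a covariate", again with an unstructured covariance and all available data. It adds that "The primary treatment comparison between LCZ696 and enalapril is to be made at Week 8 and Month 6". Section 6.4.3 schedules the KCCQ at Visits 201, 204, 206, 209, 212 and 299, that is at baseline, Week 8, Months 6, 18 and 30, and end of study.

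Both sections spell out the interactions and the covariance structure. The single baseline covariate is therefore a stated choice, not a detail left open.

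**The concern.** With treatment-by-visit in the model but no baseline-by-visit, the regression on baseline is held constant over follow-up. If the link with baseline weakens with time, a common slope is too steep at late visits, too flat at early ones, or both. The baseline variation it fails to remove goes into the residual variance at those visits, and the treatment contrast there is less precise than the same data allow.

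A changing slope is plausible in this design. Visit 101 comes before the run-in, the randomised switch and the up-titration at Week 4. The KCCQ schedule runs from Week 8 to Month 30 and beyond. At stake is a small amount of precision on key secondary comparisons in a trial of about 220 patients sized mainly on feasibility (9.7), where more patients cannot readily be added.

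**Working it through.** **What the protocol quantifies.** Its only size calculation is for the primary endpoint. It reproduces: events = 4 × (z₀.₈₀ / ln 0.80)² = 4 × (0.8416 / 0.2231)² = 56.9, or 57. That figure is unaffected here. The protocol states no SD, visit correlation or power for NT-proBNP or KCCQ, so all correlations below are assumptions.

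**Formula.** Scale each visit to unit variance. Let β_k be the true slope on baseline at visit k (the correlation with baseline) and b the common slope that generalised least squares settles on under an unstructured covariance. With complete data:

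- residual variance with visit-specific slopes: 1 − β_k²
- residual variance with the common slope: 1 − β_k² + (β_k − b)²
- variance inflation of the contrast at visit k: (β_k − b)² / (1 − β_k²)

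Equal slopes give β_k = b and zero inflation.

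**Assumed decay.** Correlation between two measurements d weeks apart = a + (c − a) × exp(−d/h). Three patterns (a, c, h): A (0.7, 0.9, 20), B (0.5, 0.9, 20), C (0.3, 0.9, 26).

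**NT-proBNP, worked for pattern B.** Visit 101 is 2 weeks before randomisation, so Weeks 4 and 8 and Month 6 are 6, 10 and 28 weeks from baseline.

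- Slopes: 0.5 + 0.4·exp(−0.3) = 0.796; 0.5 + 0.4·exp(−0.5) = 0.743; 0.5 + 0.4·exp(−1.4) = 0.599. Common slope b = 0.737.
- Month 6: (0.599 − 0.737)² = 0.0190; 1 − 0.599² = 0.641; inflation 0.0190 / 0.641 = 3.0%.
- Week 8: (0.743 − 0.737)² is about 0.00004, so inflation is about 0%.

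Variance inflation for NT-proBNP:

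| Pattern | Week 4 | Week 8 | Month 6 | Month 6 if Week 2 is also modelled |
|---|---|---|---|---|
| A | 0.3% | 0.0% | 1.1% | 1.6% |
| B | 1.0% | 0.0% | 3.0% | 4.5% |
| C | 1.5% | 0.0% | 5.1% | 7.4% |

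**KCCQ.** Baseline at Visit 201, same patterns. Section 9.5.1.4 does not say which visits enter the model, so both cases are shown:

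| Pattern | Week 8 and Month 6 only: Week 8 | Week 8 and Month 6 only: Month 6 | Months 18 and 30 added: Week 8 | Months 18 and 30 added: Month 6 |
|---|---|---|---|---|
| A | 0.3% | 0.6% | 1.2% | 0.1% |
| B | 0.7% | 1.8% | 3.5% | 0.3% |
| C | 1.1% | 3.1% | 7.8% | 0.2% |

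**Sensitivity to shape.** A mild assumed decline (slopes 0.70, 0.68, 0.60, with visits correlated 0.7) gives 0.8% at Month 6. A steep decline while visits stay highly correlated (0.85, 0.75, 0.50) gives more than 10% there. The documents do not say which applies.

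**Simulation with the trial's features.** 220 patients, randomisation stratified on a screening value, stratum in the model, 10% dropout, 700 repetitions, NT-proBNP at Weeks 4 and 8 and Month 6. For A, B and C, the model-based information loss at Month 6 was 1.3%, 3.3% and 5.3%, close to the formula. The loss in the empirical variance of the estimates was smaller and noisy: 0.4%, 2.4% and 0.9%. With equal true slopes, the extra terms had no measurable cost (within about 0.5%).

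**Scale.** A 3% loss of information corresponds to 0.03 × 220 = 6.6 patients. A 3% larger variance widens a confidence interval by √1.03 − 1 = 1.5%; a 7% larger variance widens it by √1.07 − 1 = 3.4%.

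**The case against.** The strongest reply is that nothing here is wrong. A repeated-measures ANCOVA with one baseline covariate, treatment-by-visit and unstructured covariance is a valid and complete specification, and model terms are often refined in the SAP, which is not at hand. That stands as far as it goes: it makes this a free improvement and not a defect. It does not remove the point, because the protocol fixes the terms itself.

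The loss is also negligible at most of the five named comparisons, and for KCCQ its size and location depend on the modelled visits. Stratifying on screening NT-proBNP already balances part of baseline, which probably explains why the empirical losses were below the model-based ones. No significance threshold or power rests on these endpoints. All of this stands and limits the importance of the point.

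Two stronger readings are tempting. A reader might infer that the plan certainly gives up a few percent of its information. The documents do not support this: they give no correlations, and the loss is zero if the slopes are equal. A reader might also infer that the missing-at-random assumption fails because the mean model is too simple. Missing at random describes the missingness mechanism and does not depend on the mean model. A misspecified mean can bias a contrast under dropout. With 8 to 11% assumed missing at Month 6, related to baseline in one arm only, the bias was about 0.13 to 0.18 standard errors; when missingness related to baseline equally in both arms, it was near zero. Nothing in the documents shows that the one-sided pattern is expected.

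**Conclusion.** The point holds as a minor efficiency improvement. Both models as listed impose a single baseline slope, and with complete data the treatment contrast remains unbiased. Under assumed, gradually decaying correlation, the variance of the contrast could be roughly 0 to 7% larger, slightly more in the steepest gradual pattern tried. For NT-proBNP this falls mainly at Month 6, with about zero at Week 8 and at most about 2% at Week 4. For KCCQ it falls at Week 8 only if Months 18 and 30 are modelled; with Week 8 and Month 6 alone it is about 1% or less at Week 8 and up to about 3% at Month 6. Every figure depends on the assumed decay, and the empirical loss under stratified randomisation may be smaller. The common slope brings no measurable compensating benefit at this sample size.

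**What to change.** Add a baseline-by-visit interaction to the repeated-measures models in Protocol 9.5.1.4 and 9.5.1.10, or in the SAP if it does not already contain one, before unblinding. Read the treatment contrasts at the named visits as already planned. Stating which visits enter each model would also settle where any difference could fall. The cost is one extra parameter per additional visit: three for NT-proBNP if Weeks 2, 4 and 8 and Month 6 are modelled, and up to four for KCCQ if end of study is a separate level. That is negligible with about 220 patients and needs no new data.
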